### Research Objectives/Background

1. Include primary, secondary, and exploratory objectives.  
**Primary goal: to evaluate whether allowing showering after a certain number of days post breast reconstruction has an effect on the infection rate**  
**Secondary goal: to evaluate whether allowing showering after a certain number of days post breast reconstruction has an effect on the quality of life of patients**
2. Include background and rationale for initiating the study. Includes pre-clinical and clinical data, current experiences with procedures, drug, or device, and any other relevant information to justify the research.  
**Currently, there is a lack of consensus on best practices regarding showering with drains in place following first stage breast reconstruction. There is anecdotal concern for an increased risk of Surgical Site Infection (SSI), but the current literature to support this is lacking. There is also some evidence that showering with drain tubes in place has no increase risk of infection. It is not known whether showering with drain tubes decreases the risk of SSI. Surgical drains can remain in place upwards of two to three weeks in the postoperative period. The recommendation not to shower until drain removal can present a significant challenge for patients resulting in distress and decreased quality of life. Our study will assess the infection rates in patients allowed to shower at 48 hours postoperatively compared to those not showering until drains are removed. Our hypothesis is that this study will reveal no difference in the rates of SSI and improved quality of life in patients who are allowed to shower with drain tubes in place.**

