### Number of Subjects

1. Include anticipated enrollment number in this study. Include a break-down in numbers if there is more than one subject population.  
**Our goal is to achieve an  $n$  of 100 with 50 patients allocated to the experimental arm (showering at 48hrs) and 50 allocated to the control (current standard of care).**
2. Include statistical analysis or other justification for the number of subjects enrolled.  
**An  $n$  of 100 provides us with adequate power for a statistically significant difference between subject arms to be detected if one is present.**

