### **Anticipated Benefits**

1. Include both direct and indirect benefits for either the individual or society.  
**Direct benefits include better understanding factors that contribute to SSI in the postoperative period following first stage breast reconstruction. Indirect benefits include the ability to change current standard practice regarding showering with drains to improve patient quality of life.**

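### The hypothesis of no SSI difference does not match the protocol's own primary goal or its difference-based sample size, and no acceptable excess of SSI is stated

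*Protocol*

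**What the plan says.** Research Objectives/Background gives the primary goal as "to evaluate whether allowing showering after a certain number of days post breast reconstruction has an effect on the infection rate". The background text in the same section closes with an expectation: "Our hypothesis is that this study will reveal no difference in the rates of SSI". The second half of that sentence expects better quality of life with showering and is not at issue here.

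Number of Subjects sets 50 patients per arm and says that this number "provides us with adequate power for a statistically significant difference between subject arms to be detected if one is present". It gives no SSI rate, effect size, significance level or numerical power.

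Study Procedures/Design/Treatment Plan, item 3, again describes the aim as finding out whether there is an effect on infection. The stopping rule in Potential Risks/Adverse Events, item 2, looks for a clear statistical benefit in one arm. Anticipated Benefits lists, as an indirect benefit, "the ability to change current standard practice regarding showering with drains to improve patient quality of life". Nowhere does the protocol mention non-inferiority, equivalence, a margin or a largest tolerable excess of SSI.

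**The concern.** A test for a difference can provide evidence that the arms differ. It cannot provide evidence that they do not, because failing to reject is what a small trial tends to produce whether or not an excess exists. Evidence for no important excess needs a stated limit and a confidence interval that stays below it. This protocol hypothesises the absence of a difference, plans its numbers around finding one, and states no limit. A non-significant test would then seem to confirm the hypothesis.

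At stake is the inference about infection. The protocol itself says in its risk section that infection risk with showering could go either way or be unchanged. If a non-significant comparison were taken as support for showering with drains in place, practice could shift on data that still allow a substantial excess of SSI.

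**Working it through.** **The plan's own figure.** The 100 patients cannot be reproduced, because none of the inputs to a sample-size calculation is stated. What can be checked is what 50 per arm would allow one to conclude. All SSI rates and margins below are assumptions. Differences are showering minus control.

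**Step 1. Identical observed rates.** The Newcombe 95% interval combines the Wilson limits (l, u) of each arm:

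lower = d − √[(p1 − l1)² + (u2 − p2)²]; upper = d + √[(u1 − p1)² + (p2 − l2)²].

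Wilson 95% limits with n = 50: 2/50, 1.10% to 13.46%; 5/50, 4.35% to 21.36%; 10/50, 11.24% to 33.04%.

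| Observed SSI, each arm | Half-width (points) | Result |
|---|---|---|
| 2/50 (4%) | √(9.46² + 2.90²) | ±9.9 |
| 5/50 (10%) | √(11.36² + 5.65²) | ±12.7 |
| 10/50 (20%) | √(13.04² + 8.76²) | ±15.7 |

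Set against the observed control rate, a tie at 4% leaves room for 4 + 9.9 = 13.9%, and a tie at 10% for 10 + 12.7 = 22.7%. Both are more than double. A tie at 20% leaves room for 20 + 15.7 = 35.7%, a large excess but short of double.

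**Step 2. An observed doubling.** Take 10/50 with showering against 5/50 without, so d = 10 points.

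- Lower: 10 − √(8.76² + 11.36²) = 10 − 14.3 = −4.3.
- Upper: 10 + √(13.04² + 5.65²) = 10 + 14.2 = +24.2.
- Fisher exact p = 0.26.

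With 11/50 against 5/50, p = 0.17 and the interval is −2.6 to +26.4. Both results are non-significant at two-sided 0.05, although SSI at least doubled in the sample.

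**Step 3. How often a true doubling would be missed.** Exact power of Fisher's test, two-sided 0.05, 50 per arm: 6.3% for 5% to 10%; 19.5% for 10% to 20%; 35.4% for 15% to 30%; 51.5% for 20% to 40%. At control rates of 5% to 15%, non-significance is the more likely outcome even when SSI truly doubles.

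**Step 4. Could a margin added later rescue 50 per arm?** Assume equal true rates p, one-sided 0.025 and, for illustration only, a margin of 10 points. Then SE = √[2p(1 − p)/50], power = Φ(0.10/SE − 1.96), and the number per arm for 80% power is (1.960 + 0.842)² × 2p(1 − p)/0.10², rounded up.

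| Assumed SSI rate | SE | Power at 50 per arm | Per arm for 80% power |
|---|---|---|---|
| 3% | 0.0341 | 83.4% | 46 |
| 5% | 0.0436 | 63.1% | 75 |
| 10% | 0.0600 | 38.5% | 142 |
| 15% | 0.0714 | 28.8% | 201 |
| 20% | 0.0800 | 23.9% | 252 |

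Only the 3% row passes 80%, and there a 10-point excess would take the rate from 3% to 13%, more than four times as high. With a 5-point margin, power at 50 per arm is 31.0% at a 3% rate, 20.8% at 5%, 13.0% at 10%, 10.4% at 15% and 9.1% at 20%. The removal criteria in Study Procedures, item 4, could leave fewer than 50 per arm and lower these figures further.

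**The case against.** The strongest reply is that the design is largely consistent. The primary goal, the restated aim in Study Procedures, the sample-size statement and the stopping rule all ask whether there is a difference. Only one sentence of expectation in the background departs from this, and investigators often say what they expect without making it a decision rule. That stands, and it locates the fault: the hypothesis sentence is out of line, not the objective.

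A reader might infer that the protocol commits itself to treating a non-significant test as proof of safety, or to changing practice on that basis. The documents do not support this. No section says so, and Anticipated Benefits names practice change only as an indirect benefit, without tying it to a null result. What remains is that the protocol gives no other path from the data to its hypothesised conclusion.

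It can also be said that interval reporting and the wording of a non-significant result are commonly left to the statistical analysis plan, which is not available here. Their absence alone is therefore not the fault. But the hypothesis and the rationale for 100 patients are fixed in the protocol, and a later plan could add a margin without making 50 per arm adequate for it.

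Finally, the magnitudes follow from the small sample and so overlap with any criticism of the power statement. That is fair as to the numbers. The logical point is separate: rewording or quantifying the power statement would still leave a hypothesis of no difference with no limit to judge it by.

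**Conclusion.** The point holds in this form: the hypothesis does not match the primary goal or the basis of the sample size, and no acceptable excess of SSI is stated. At 50 per arm, equal observed rates of 4% to 20% leave an excess of about 10 to 16 points unexcluded, and an observed doubling from 10% to 20% is non-significant. A non-significant result could thus coexist with SSI more than doubling. These sizes rest on assumed SSI rates, 50 analysed per arm, 95% intervals and a two-sided 0.05 test, none of which except the allocation is given in the protocol.

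It would go too far to say that the trial cannot support a safety claim under any circumstances. That depends on the true rate and on a margin nobody has stated; a very low rate with a wide margin would be within reach. At SSI rates of 5% or more, 50 per arm falls short of 80% power for either illustrative margin. The fault is worth correcting before enrolment but does not invalidate the trial.

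**What to change.** 1. In Research Objectives/Background, reword the SSI hypothesis as estimating the difference in SSI risk between the arms. The quality-of-life expectation can stay.
2. State that the SSI conclusion will rest on the risk difference with its 95% confidence interval, and that a non-significant test will not be reported as showing no difference or as showing that showering is safe.
3. In Anticipated Benefits, limit the claim to informing practice or a larger trial.
4. If the sponsor wants to claim no important excess, state and justify the margin before enrolment, and make the claim only if the upper confidence limit lies below it. The protocol should then acknowledge the low power of 50 per arm at most plausible rates, or recalculate the sample size.

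Items 1 to 3 are wording changes and need no extra patients; the price is a more modest conclusion. Item 4 is not free: with the illustrative 10-point margin, 80% power needs 75, 142 or 252 per arm at SSI rates of 5%, 10% or 20%.

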### Drugs/Biologics/Devices

1. Include the product, dose, route, and regimen.: **N/A**
2. Include the rationale for choosing the drug/biologic and dose, or for choosing the device to be used: **N/A**

3. Include the standard reference therapy against which the study product is being compared, or if the reference is a placebo. Include justification for inclusion of a placebo or non-treatment group: N/A
4. Include justification and safety information: N/A
5. If an IDE (for investigational devices) or IND (for investigational drugs) is not necessary, provide justification.: N/A

### Recruitment Process

1. Describe the recruitment process; including how and where recruitment will take place.  
**Recruitment will take place in the UMHC PRS clinic. Patients scheduled to receive first stage breast reconstruction will be asked for their participation in the study and randomized to either the control or experimental arm.**
2. Describe any screening/baseline procedures.  
**Patients will be assessed via physical exam and obtainment of past medical history to determine need for first stage breast reconstruction.**

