### Consent Process

1. Describe the consent process; including who will be approached for consent and what type of consent will be obtained from each subject population, if there is more than one.  
**A written consent using the IRB consent template will be used for each new patient undergoing implant-based breast reconstruction. Consent will be obtained by any of the staff included in the IRB application at the initial pre-operative appointment ranging from one week to one month pre-op. Written consent will then be obtained and stored in the medical record.**

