### Study Procedures/ Design/Treatment Plan

1. Include study procedures/design/plan; include the sequence and timing of study procedures (distinguish research procedures from those that are part of routine care). Include study duration and number of study visits required.  
**Study will last 90 days. Patient's will be admitted to the hospital following surgery if the reconstruction takes place immediately following mastectomy. If the reconstruction does not occur at the same time as mastectomy, patients are not admitted. This is part of our routine care. Regardless, they will be evaluated on post operative day one. Following the initial post operative day one visit, patient's will be evaluated on a weekly basis for 90 days. Vitals will be taken at the visits, and routine physical examination (including evaluation for surgical site infection) will be performed. Patient reported outcomes will be obtained at these visits as well. We will also ask patients if they have been showering or not and if so how often. This will be documented. For example: patient evaluations will be as follows:**
  - One-month preoperative visit
  - Day of surgery
  - Post Operative Day one evaluation (In the hospital or clinic)
  - Clinic Visit 1: One week after surgery
  - Clinic Visit 2: Two weeks after surgery

**These visits will not differ from our routine care. At the conclusion of 90 days patients will receive a survey asking if drain care and the ability or inability to shower with drain tubes in place adversely affected their quality of life.**

2. Blinding, including justification for blinding or not blinding the trial. Describe unblinding procedures.  
**The study will not be blinded. Participants will be randomly assigned to treatment arm. Researchers and patients will know which arm they are assigned to.**
3. Justification of why participants will not receive routine care or will have current therapy stopped.  
**The goal of the study is to determine if there an effect on infection rate with allowing patients to begin showering 48 hours after surgery rather than waiting to shower until drains are removed. There is no definitive literature on this, and the care of surgical drains is ultimately decided by the surgeon. There is currently no defined standard of care regarding showering with surgical drains in place.**

4. Definition of treatment failure or participant removal criteria.  

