**Data must be kept for seven years after the study has been completed.**

### Potential Risks/Adverse Events

1. Describe reasonably foreseeable risks or discomforts to the subjects and steps to minimize risks.  
**The study involves minimal risks and steps will be taken to mitigate these risks. Risks include: soft tissue infection, breast implant infection, decreased quality of life, breach of confidentiality. Infection risk may be higher, lower, or the same in those who allowed to shower with drains in place compared to those not allowed to shower. There is a lack of literature to support increased risk of infection with showering with JP drains in place. Timing of showering is ultimately surgeon dependent. Regardless, this risk will be mitigated by continuing with sterile surgical technique with proper prepping and draping of the patient as well as sterile placement of drain tubes intra-operatively. Patient's will also be instructed to not soak in water, such as in a bath tub. Rather, they will be instructed to shower and let water run over the drain tube sites. Patients will be immediately treated if there any signs of infection. In terms of decreased quality of life, patients who will not be allowed to shower until drain tubes are removed will be allowed to sponge bath to help mitigate any discomfort. The final risk is possible breach of confidentiality. These risks will be minimized by de-identification of data collected on a separate file, a link between randomly assigned number and identifiable data will be listed. All data collected will be secured on a password protected excel spreadsheet. No persons outside those listed. Accidental removal of a surgical drain is not increased by this study. It is part of our routine care to suture the drain tubes to the skin. Accidental dislodgement of drains is an extremely rare event and is part of the normal post operative surgical risks.**
2. Describe any stopping rules.  
**We would immediately withdraw patients per their request. We would also stop the study all together if there was a clear statistical benefit in one of the study arms.**
3. Include the plan for reporting unanticipated problems or deviations. This plan must include a five-day reporting requirement to the IRB once becoming aware of an event.  

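### On its natural reading the protocol randomises openly at pre-operative recruitment, although the arms do not differ until 48 hours after surgery; allocate on post-operative day one instead

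*Protocol*

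**What the plan says.** Protocol, Recruitment Process, item 1: "Recruitment will take place in the UMHC PRS clinic". Patients who are scheduled for the operation "will be asked for their participation in the study and randomized to either the control or experimental arm". The invitation and the randomisation stand in one sentence, and no visit or day is named for the allocation itself.

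Protocol, Consent Process, item 1: consent is obtained "at the initial pre-operative appointment ranging from one week to one month pre-op".

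Protocol, Research Objectives/Background: the comparison is of "patients allowed to shower at 48 hours postoperatively compared to those not showering until drains are removed". Up to 48 hours after surgery the two arms are treated alike.

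Protocol, Study Procedures/ Design/Treatment Plan: there is no blinding, and "Researchers and patients will know which arm they are assigned to" (item 2). Item 1 provides an evaluation for every patient, admitted or not: "Regardless, they will be evaluated on post operative day one".

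Protocol, Inclusion/Exclusion Criteria, item 2, bars patients with wounds, infection or antibiotic use in the preceding ten days. It does not say as of which date this is judged. The removal criteria concern only showering and adherence to post-operative instructions. They do not cover an operation that is cancelled or changed.

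**The concern.** Allocation is best made as close as possible to the moment the arms part. Here nothing requires the arm to be known before the operation, yet the protocol appears to assign it days or weeks earlier, in an open trial. Three things are then exposed.

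- **Conduct of the operation.** The primary outcome is infection. The risk section relies on sterile technique and "sterile placement of drain tubes intra-operatively" to limit it, and the background records anecdotal worry that showering with drains raises infection risk. Someone who shares that worry and knows the arm could take more care in one arm than in the other. The resulting bias would be systematic, and a larger sample would not remove it.
- **Eligibility.** A ten-day antibiotic restriction checked at a visit at least a week before surgery says nothing about the days that follow.
- **Losses.** The contrast exists only once surgery has taken place and a drain is in. Patients who never reach that point are already randomised. A patient who dislikes the assigned arm also has time to withdraw before the operation.

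**Working it through.** The plan has no figure on this point to reproduce. It gives no infection rate, cancellation rate or dropout allowance. The timing follows from the text; the sizes below rest on stated assumptions.

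**1. Interval from allocation to divergence**, if allocation is made at the consent visit.
- Inputs: consent one week to one month before surgery (Consent Process), i.e. 7 to 31 days; divergence at 48 hours, i.e. 2 days (Research Objectives/Background).
- 7 + 2 = 9 days; 31 + 2 = 33 days (32 for a 30-day month).
- Allocation after surgery and before 48 hours: at most 2 days.

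**2. Eligibility window.** Input: the ten-day antibiotic look-back (Inclusion/Exclusion Criteria, item 2). A check made 7 days before surgery covers days 17 to 7 before the operation. One made 31 days before covers days 41 to 31. The last 7 to 31 days before surgery are unchecked unless the check is repeated, and the protocol states no repeat.

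**3. Losses between allocation and surgery.** Assumed 3-10%: 100 x 0.03 = 3 and 100 x 0.10 = 10 patients. Each lost patient is 1/50 = 2% of an arm.

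For the cost in precision, take any effect detectable with 80% power at 50 per arm (two-sided 5%, pooled two-proportion normal approximation; for example 10% against 32.7%):

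| Assumed loss | Patients per arm | Power | Randomised to keep 100 operated |
|---|---|---|---|
| 0% | 50 | 80% | 100 |
| 5% | 47.5 | 78% | 100/0.95, rounded up: 106 |
| 10% | 45 | 76% | 100/0.90, rounded up: 112 |
| 20% | 40 | 70-71% | 100/0.80 = 125 |

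The 80% is a reference point for this illustration. The protocol claims only adequate power and gives no basis for it.

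**4. Shift from arm-dependent precautions.** Assumptions: baseline infection risk 5-20%; in 10-30% of showering-arm operations an added precaution halves the risk. Shift = baseline risk x share of operations x 0.5.

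| Baseline risk | 10% of operations | 30% of operations |
|---|---|---|
| 5% | 0.05 x 0.10 x 0.5 = 0.25 points | 0.75 points |
| 10% | 0.50 points | 1.5 points |
| 20% | 1.0 points | 0.20 x 0.30 x 0.5 = 3.0 points |

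One patient in an arm of 50 is 1/50 = 2 points. Most of this range is therefore below one patient per arm, and the upper end is 3.0/2 = 1.5 patients.

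**The case against.** The strongest reply is that the timing is pieced together. The recruitment sentence gives an order of events without a date, the week-to-month window belongs to consent, and the blinding item says only that assignment is random. That is correct: the protocol does not state that allocation happens at the consent visit, and it does not exclude a later point. Pre-operative allocation nevertheless remains the natural reading of the only sentence that places randomisation, because it concerns patients still scheduled for surgery and sits with their invitation in the clinic. If a later point is intended, that sentence needs amending anyway.

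A reader might go further and infer that surgeons do operate knowing the arm and adjust their technique. The documents do not support that. They say researchers and patients know the arm, and do not say whether the operating surgeon is told beforehand. The risk section describes the same sterile approach for everyone. The remark that "the care of surgical drains is ultimately decided by the surgeon" concerns drain care and does not mention operative technique. What stands is that nothing in the protocol prevents the arm from being known in the operating room.

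It is also fair that cancellation has no stated link to arm, so the expected cost of such losses is mainly precision, and that the analysis of randomised but unoperated patients may be set out in a statistical analysis plan that is not at hand. Their absence from the protocol's analysis text is not part of this point. The moment of allocation, however, is a protocol matter.

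Finally, day one allocation leaves all later care and infection assessment open, and it adds a drain-in-place condition that is not among the present criteria. Both observations stand. The condition does follow from the comparison itself, since the control instruction is defined by drain removal.

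**Conclusion.** The point holds as a design weakness that is cheap to correct. Read naturally, the protocol randomises about one week to one month before surgery, and roughly 9 to 33 days before the arms diverge, in an open trial. This permits knowledge of the arm during the operation and puts into the randomised set patients who may never enter the contrast or may no longer be eligible. It is not shown that either has happened or will.

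The size cannot be derived from the protocol. Under the assumptions in the working, 3 to 10 of 100 patients would be lost between allocation and surgery, and the infection comparison would shift by about 0.25 to 3 points, mostly less than one patient per arm. Confidence is moderate, because the date of allocation and the surgeon's knowledge of the arm are both inferred. The case for change rests on how little it costs to remove both exposures. It does not rest on a demonstrated large bias.

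**What to change.** Keep consent at the pre-operative appointment. Amend Recruitment Process, item 1, to state that the allocation is generated or opened only after surgery, at the existing post-operative day one evaluation and before 48 hours, for patients who:

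- had the planned operation;
- have a drain in place; and
- met the wound, infection and antibiotic restrictions as of entry to surgery.

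Count the 50 + 50 from that point. State that consented patients who do not reach it are not randomised, and report their number and the reasons.

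Cost: showering instructions are given on day one instead of before the operation; the allocation must be accessible at that visit, in hospital or in clinic; and the restrictions must be confirmed again at surgery. More patients may need to be consented to reach 100 randomised, but no visit is added. The change leaves both showering regimens as they are. It does not address bias from open post-operative care or unblinded infection assessment, which needs separate measures.
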